6. Medically stable with no contraindications to MRI.
7. Have not been treated with lipid-lowering therapy for more than one year.

Exclusion Criteria

1. Younger than 21 years of age.
2. Have pacemakers or metal implants.
3. Have immediate plans for carotid endarterectomy.
4. History of drug or alcohol abuse in last five years.
5. Active liver disease or hepatic dysfunction as defined by elevations of more than 1.5 times the ULN for AST or ALT.
6. Serum CK \geq three times ULN
7. GFR \leq 59 mL/min/1.73 m² prior to randomization.
8. Bowel obstruction.
9. Hypertriglyceridemia (serum triglycerides \geq 500 mg/dL).
10. Peptic ulcer disease.
11. A fasting glucose level \geq 150 mg/dL or HbA1c \geq 8%.
12. Uncontrolled hypertension as defined as either a systolic reading of \geq 200 mmHg and/or a diastolic reading of \geq 95 mmHg.
13. Women who are or have plans of being pregnant in the future.

B.3. Screening and Eligibility Assessment:

All subjects who are interested in participation will receive a telephone screening using an IRB-approved script to get a general idea of subject's demographics and any major inclusion/exclusion criteria. Potential subjects will be invited to one of the 5 study locations as described above for their screening visit. Subjects will be given a screening consent by the study coordinators; the investigators will follow up with additional questions. If subjects do not have further questions and are willing to be screened for the study, screening procedures will be carried out per protocol. Please note that subjects do not need to stop their statin therapy for study screening. Adjusted ApoB levels will be calculated based on the type and dose of statin that subjects are receiving. Carotid MRI and/or ultrasound exams will be performed using the pre-designed

imaging protocol that will be provided later under MRI scan protocol and ultrasound sub-study protocol.

After receiving all the screening information, subject's eligibility will be assessed by a team of investigators and study coordinators. A checklist on inclusion and exclusion criteria will be completed and signed by one of the investigators including Drs. [name], [name], [name], [name], or [name].

All screened subjects will be given the screening results and will be informed regarding their eligibility for the study.

B.4. Subject Enrollment:

The qualified subjects will be invited to take the next step - baseline evaluation and study randomization.

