Subjects who are willing to consider participating in the study will be given a main study informed consent by the study coordinators; the investigators will follow up with additional questions. The informed consent process will take as long as needed. The following items will be discussed in detail: study purpose, procedures, what randomization means, medication(s), any possible side effects, anticipated risk and discomfort, subject's right to withdraw from the program at any time, and additional questions.

After obtaining the study consent, vital signs including blood pressure, heart rate, weight, height, and waist circumference will be taken. Blood sample will be collected for laboratory measurements required by the study design. Canadian Angina Function Class will be used to assess subjects' ischemia status. Subjects will be also asked to confirm if they have on-going conditions such heartburn, nausea, intestinal gas, muscle aching, flushing, glucose increase and fatigue. The baseline evaluation will be by a team of investigators including Drs. [name], [name], [name], or [name] and coordinators and/or nurses at each site.

B.5. Randomization:

As mentioned in the study design, subject's lipid therapy will be randomly assigned to one of three treatment groups: (1) single therapy - atorvastatin alone,; (2) double therapy – atorvastatin plus Niacin (2 g/day); (3) triple therapy – atorvastatin, Niacin plus ezetimibe (10 mg/day). .

This randomization will also be stratified based on (a) gender, (b) diabetes (yes or no), (c) smoking (yes in past 2 months or no), and (d) triglycerides ≥ 200 mg/dl (yes or no) to ensure the clinical and lipid characteristics will evenly distributed among the 3 treatment groups.

Randomization will be conducted using a computer program with information entered by the study coordinators.

B.6. Atorvastatin Dosage Determination and Adjustment:

The first dose of Atorvastatin is determined based on the following conditions:

- (1) Subjects post Acute Coronary Syndrome (ACS) will continue their high dose atorvastatin, 40-80 mg daily, prescribed by their physicians. If a subject is taking a different statin, such as simvastatin, the subject will discontinue simvastatin and begin atorvastatin, 40-80 mg, if tolerated.

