This dosing-up can last as long as 6 months based on how well the subjects can tolerate each dosage level.

Aspirin (81-325mg) is recommended 30 minutes before taking niacin.

B.8. Study Medication Information and Instruction

In addition to the medication information listed in the study informed consent form, we will also provide subjects a separate document as shown below with the drug

information for the 3 medications used in CPC. **Pertinent Medication Information for the Carotid Plaque Composition by MRI During Lipid-lowering Study**

There are three study medications used in this study.

1. Lipitor (atorvastatin)

A member of the drug class known as statins, used for lowering cholesterol. Lipitor helps decrease the amount of LDL or ‘bad’ cholesterol in the blood by blocking an enzyme called HMG-CoA reductase, an enzyme that makes cholesterol. Statins reduce total cholesterol, as well as LDL-cholesterol, in the blood, which slows the progression of heart disease. Lipitor is generally well tolerated. In less than 1% of people, it may cause muscle aches or certain abnormalities of muscle-related blood tests. These problems are rare and are reversible by stopping the medication. In the study, blood sugar, liver function and muscle tests are taken often.

2. Slo-Niacin (slow-release niacin)

Slo-niacin is a medication used to raise levels of HDL or ‘good’ cholesterol and lower triglycerides. The risks from Slo-Niacin include a warm flushing sensation that occurs shortly after taking the medication, which may be difficult to tolerate. Slo-niacin may uncommonly (2-4% of users) cause a skin rash, increased blood sugar or cause mildly abnormal liver tests. Fatigue, nausea, loss of appetite and muscle aches may be drug-associated side effects, although generally rare.

3. Zetia (ezetimibe)

Ezetimibe works by preventing cholesterol absorption in the intestine. It is generally well tolerated. Side effects may include headache, dizziness, diarrhea, sore throat, runny nose, sneezing and joint pain. Rare side effects include hives, rash, itching or swelling, hoarseness, upset stomach, tiredness, unusual bleeding, pain, flu-like symptoms, muscle pain or weakness or chest pain.

The medication instruction sheet as shown below is also provided to all subjects at the study medication initiation visit.

Directions for CPC Study Medication Schedule

Morning Dosing Directions (AM):

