Take One ezetimibe pill and 1-2 pills of Slo-niacin (or half of the daily dose indicated on the bottle) as instructed, with breakfast.

Evening/Night Dosing Directions (PM):

Take 1-2 Atorvastatin pills with dinner, as indicated on the bottle. Take 1-2 pills of Slo-niacin (or half of the daily dose indicated on the bottle) with dinner or before bed.

Valuable Information:

Niacin can sometimes cause a flushing feeling when you first start taking it. If this occurs, there are a few suggestions to help stop or reduce this feeling. The flushing feeling usually goes away over time if you continue to take niacin.

Some helpful ideas for reducing niacin-related flushing:

1. Take your medication in the morning and right before bed.
2. If you use a daily aspirin, take it 30 minutes before your niacin (either morning or evening). Do not take more than 325 mg Aspirin daily without first talking to your doctor.
3. 'Flushing' is reduced by food in your stomach. Enjoy a low-fat snack before you take niacin. An ounce of cheese with a few crackers, a cup of milk or yogurt with fresh fruit are a few examples.
4. Avoid hot drinks, alcohol and spicy foods with dinner as this can sometimes encourage flushing from niacin.

The study medication dispensing process is described under B.11.

B.9. Clinical and Laboratory Follow-up Procedures:

After randomization, the study subjects will be seen monthly for six months and bi-monthly for the remaining 30 months of the 36-month protocol. A total of 22 visits will be conducted for this study as shown in the procedure table below. This clinic visit protocol is developed based on the successful FATS and HATS (RO1 HL49546) clinic visit models. The clinical visits will be done by a team of investigators, coordinators and nurses as well at each of 3 study sites.

Participants who complete the first 3 years of the study and are willing to continue on the randomized therapy and will be followed every 4 months for up to 11 more years.

Table. Clinical Follow-up Protocol

Visit	Entry Criteria	Con-sent	Med. Hx	Family Hx	Vital Signs	Diet Counseling	AE/ Side Effects	Drug Disp.	Com-pliance	Safety Moni-toring	Meds Adj.
Screening	X	X			X						
Baseline		X	X	X	X	X		X			
Non-blood draw visits*					X	X	X	X	X	X	X
Blood draw visits**					X	X	X		X	X	

*: C1, 2, 4, 6, 10, 14, then every 4 months up to C130. **: C3, 5, 8, 12, then every 4 months up to C132.

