At these visits, subjects will undergo questioning about side effects and symptomatic state, and vital signs will be taken. At approximately 60% of the visits, blood will be drawn (<50 ml). The Table below provides the laboratory parameters collected/measured in this study.

Table. Laboratory Measurement Schedule for the Carotid Plaque Composition Study

Visit	S C R.	C o	C 3/ 5/ 8	C 12	C 16/ 20	C 24	C 28/ 32	C 36	Non-annual Visits C40/44/52/56/64 /68/76/80/88/92 /100/104/112/116 /124/128	Annual Visits C48/60/ 72/84/96/ 108/120/132	T X
TC/TG/LDL/ HDL/VLDL	X	X	X	X	X	X	X	X	X	X	X
HDL2&3/IDL/ LDLT/HDLT		X		X		X		X		X	
ApoB, A1, A2, ApoE, Lp(a)	X	X		X		X		X		X	
AST/ALT, CPK		X	X	X	X	X	X	X	X	X	X
BILI/ ALK PHOS/T4/TSH		X									
Creatinine/ Uric Acid		X		X		X		X		X	

Fasting glucose/ HbA1C**	X	X	X	X	X	X	X	X	X	X	X
Insulin/ Fibrino./ HsCRP		X		X		X		X		X	
Plasma storage		X		X				X		X	

*: SCR=screening; Co = baseline; C3, 10, 24, 36,..... = 3, 10, 24, 36,..... months in the study. TX = test for possible side effects of the study treatment. **: This schedule is for diabetic subjects. For non-diabetic patients fasting glucose is measured at S, Co, C12, C24, C36, C48, C60, and every 12 months up to C132.

Dietary counseling will be targeted at weight reduction with goals based on the level of obesity, with additional emphasis on the use of mono-unsaturated fats in a fat-limited (25-30%) diet. Dietary counseling will be provided to subjects by a certified research dietitian.

One week in advance of the next scheduled visits, subjects will receive a form letter from the study coordinators reminding them of the date and time, whether to fast, and to return unused drug supplies. One or two days before the visit they will again be reminded by telephone call from research assistance or the study coordinators, and the visit confirmed or changed. All scheduling is initiated by a computer program with capability to shift dates, making the associated adjustments in compliance calculations and drug distribution. Each clinical visit will take about 30 minutes.

B.10. Study Medication Dispensing

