All three medications are FDA approved drugs. Pfizer, Upsher-Smith, and Merck, Sharp and Dohme Corp are the three companies providing the medications (atorvastatin, Niacin, and ezetimibe). A drug supply record on each medication keeps tracking the quantity requested and received. All medication is stored at Harborview Investigational Drug Services (HMCIDS), as well as all documentation of drug dispensing.

With instruction from the UWMC Investigational Drug Services and Harborview Investigational drug Services, a study medication dispensing procedure has been developed as following.

(1) A medication card as shown below with the study name, drug information, and emergency contact information will be provided to each enrolled subject at the study medication initiation visit and repeat on their annual visits.

Study Name: Carotid Plaque Composition
Study Investigator: [name] [contact])
Study Coordinator: [name]
1. Lipitor (atorvastatin): 10-80mg/day

2. Slo-niacin (niacin): 1.5-2g/day
3. Zetia (erxetimibe) 10 mg/day

(2) The medication bottles/kits will be labeled with (a) study name, (b) subject name, (c) subject Harborview ID number, (d) medication name, (e) dispensing date, (f) expiration date, (g) total quantity, (h) instruction, and (i) a federal statement limiting use to the given study.

(3) For each enrolled subject at each scheduled study visit, a study medication prescription which is signed by the study doctor will be generated from our computer system based on the randomization, atorvastatin dosage determination and niacin dosing-up schedule, and duration between visits.

(4) Prescription requests are delivered to HMCIDS prior to the study visit and are then dispensed by HMCIDS.

(5) Each medication dispensing record will be saved in the subject medication folder.

(6) Medications will be dispensed to subjects in person at the end of each scheduled visit. All medication information and instruction will be reviewed with the subject at time of dispensing by an investigator.

(7) Subjects will receive two pill organizers, one for ezetimibe and niacin taken in the morning and one for atorvastatin and niacin at bed time, to help them to remember to take the study medications. We will also recommend placing the morning pill organizer in the kitchen and the night pill organizer maybe in the bathroom, this will help subjects to link the medication taking with their routine activities for optimal compliance.

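### AST/ALT and CK decide exclusions 5 and 6 but are first scheduled at baseline, after eligibility sign-off, and no text holds randomisation or first dispensing for the results

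*Combined protocol and SAP*

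**What the plan says.** Exclusion 5 in B.2 reads: "Active liver disease or hepatic dysfunction as defined by elevations of more than 1.5 times the ULN for AST or ALT". Exclusion 6 removes subjects with serum CK at or above three times ULN. Neither criterion says when the value must be obtained.

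B.3 places the eligibility decision at the end of screening: "After receiving all the screening information, subject's eligibility will be assessed by a team of investigators and study coordinators". The checklist is completed and signed there, and subjects are told whether they qualify. B.4 then begins: "The qualified subjects will be invited to take the next step - baseline evaluation and study randomization". After main consent, B.4 adds: "Blood sample will be collected for laboratory measurements required by the study design". Randomisation follows in B.5, with no laboratory condition attached.

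Two tables in B.9 set the timing:

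- In "Table. Clinical Follow-up Protocol", Entry Criteria is marked only in the Screening row, and Drug Disp. is marked in the Baseline row.
- In "Table. Laboratory Measurement Schedule for the Carotid Plaque Composition Study", the AST/ALT, CPK row is empty at SCR and marked from C0 onward.

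B.10 item 3 says prescriptions are generated "based on the randomization, atorvastatin dosage determination and niacin dosing-up schedule, and duration between visits". No enzyme result is among those inputs. E.3 has coordinators review laboratory results on receipt and alert the safety monitor to abnormal ones, with action taken under the safety monitoring rules. Those rules are in C.3.

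**The concern.** Two safety exclusions are signed off at a point where the plan has scheduled no value to judge them by. The first scheduled value comes at the visit where dispensing is also marked, and no sentence makes that value a condition for going further.

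At stake is whether a subject with raised liver enzymes or CK, whom the plan means to keep out, could be started on atorvastatin, with slow-release niacin in two of the three arms. C.3 also compares later results with baseline when judging whether study drug is the cause. A raised baseline that nobody had set against the exclusions would then serve as the reference.

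**Working it through.** No stated figure in the plan bears on this point, so the check is a count of table cells and a comparison of texts.

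**1. Is the blank at SCR real?** The laboratory table has 11 visit columns: SCR, C0, C3/5/8, C12, C16/20, C24, C28/32, C36, non-annual, annual and TX. The lipid row has 11 marks. The AST/ALT, CPK row has one empty cell, at SCR, followed by 10 marks, and 1 + 10 = 11. The cells line up, so the blank is not a column shift from the PDF reading.

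**2. Which criteria rest on a laboratory value, and when is each available?**

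| Criterion | Measure | Marked at SCR | Own timing in text |
|---|---|---|---|
| Inclusion 4 | ApoB | yes | – |
| Exclusion 5 | AST/ALT | no | none |
| Exclusion 6 | CK | no | none |
| Exclusion 7 | GFR | no (creatinine blank) | before randomisation |
| Exclusion 9 | triglycerides | yes | – |
| Exclusion 11 | glucose/HbA1c | yes | – |

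Three of the six are marked at SCR, and one (GFR) states its own timing. That leaves 6 − 3 − 1 = 2 with neither: exclusions 5 and 6, or 2 of the 13 exclusions.

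**3. Is there a later check?** B.4 draws blood and B.5 randomises, with no comparison against the exclusions in between. The prescription inputs in B.10 item 3 include no enzyme result. E.3 gives no timing relative to randomisation or first dispensing and does not refer back to exclusions 5 and 6.

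**4. What follows if drug is dispensed at baseline, before the C0 result is read?**

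- AST/ALT above 1.5 and up to 2.5 times ULN: exclusion 5 would have kept the subject out. Once treatment has started, C.3 step 4 repeats the test within a month, informs the primary care physician and keeps the subject on drug.
- AST/ALT or CK at or above 3 times ULN: C.3 step 5 reduces or stops drug and repeats the test within two weeks. What remains is that the subject has already been randomised and started.

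So the two rule sets give opposite answers for the same AST/ALT value only in the 1.5 to 2.5 band, and only when the result becomes known after the first dose.

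**The case against.** The strongest reply is that the plan leaves room for the check and the exclusions themselves demand it. Exclusion 5 has no time limit, so a C0 value known before randomisation still excludes. The blood draw in B.4 comes before randomisation in B.5. B.8 also points to a distinct occasion for starting drug: "The medication instruction sheet as shown below is also provided to all subjects at the study medication initiation visit". If that is a later visit, the C0 results could be in hand by then. Exclusion 7 shows that the SCR column is not the full list of tests needed before randomisation: creatinine is blank there too, and waiting for a C0 creatinine would bring the enzymes with it. An investigator must sign a checklist covering every criterion, and earlier values may exist in the medical records that E.2 lists as screening material. The checklist, CRF pages and procedure manual are not in the supplied text.

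Most of this stands as showing that a check is possible. None of it makes the check a requirement. B.3 has the checklist signed on screening information, the records named in E.2 concern vascular disease and carotid imaging, and D.2 allows GFR to come from a separate draw near the MRI scan.

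Two stronger readings are tempting. A reader might infer that C.3 step 4 is the plan's prescribed response to any raised C0 value. It is not: C.3 is an on-treatment rule set, its table begins at the 3-month sample, and drug that has not been started cannot be continued. A reader might also infer that ineligible subjects will be treated. The documents do not establish that results arrive after first dispensing. A Drug Disp. mark in the Baseline row need not mean the same day as the blood draw.

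**Conclusion.** The point holds as a conflict between schedule and criteria. Exclusions 5 and 6 are signed off before any scheduled AST/ALT or CK value exists, and no text holds randomisation or first dispensing until the C0 values are checked. The exposure is conditional on drug being dispensed at the baseline visit, as the clinical table shows, before the C0 result is read. In that case a subject with AST/ALT above 1.5 and up to 2.5 times ULN could start treatment and be continued on it.

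The size is 2 of 6 laboratory-based criteria. That counts criteria, not harm: the documents give no basis for estimating how many subjects would be affected. Some subjects already take a statin at screening, so atorvastatin would not be a new exposure for all of them. This is a minor patient-safety point. It should not be read as a threat to the primary endpoint, on which no effect is claimed.

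**What to change.** Either of two changes is enough:

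- Mark AST/ALT and CPK in the SCR column and run them on the blood already drawn at screening. The B.3 checklist can then be signed on actual values. The cost is two inexpensive assays (AST/ALT and CPK) per screened subject.
- Add a sentence to B.4 or B.5 requiring C0 AST/ALT and CK to be compared with exclusions 5 and 6, and the checklist confirmed, before randomisation and first dispensing. This needs no extra assay, only a short wait for the results.

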- (2) In subjects without ACS, first dose of atorvastatin is determined based on subjects' LDL-C levels at screening visit. The adjusted LDL-C level can be calculated based on the type of statin and dosage that subject is currently taking. If LDL-C \geq 110 mg/dl, atorvastatin 40 mg daily will be initiated. If LDL-C < 110 mg/dl, atorvastatin 20 mg daily will be initiated.

The treatment target for LDL-C will be \leq 80 mg/dl for the single and double therapy groups and \leq 60 mg/dl for the triple therapy group. In order to reach the LDL-C target, atorvastatin titration during the study will be conducted as followings:

- (1) Titration up: At 3 month follow-up visit, a blood sample is taken and LDL-C assessed. If subject's LDL-C did not reach the predefined target of \leq 80 mg/dl for single and double therapy groups or \leq 60 mg/dl for the triple therapy group, the atorvastatin dose will double. This process will be repeated at 5, 8 and 12 months and every 4 months after through out the study. 80mg atorvastatin is the highest possible dose that will be administered.
- (2) Titration down: At 3 month follow-up visit, a blood sample will be taken and LDL-C assessed. If subject's LDL-C < 40 mg/dl and > 25 mg/dl with normal AST/ALT lab values and does not report nausea or fatigue, careful monitoring will be conducted. No change will be made in the atorvastatin dosage. If subject has symptoms of fatigue and/or nausea and/or AST/ALT elevation per safety protocol, atorvastatin will be halved or stopped depending on the decision of the investigator. If subject's LDL-C < 25 mg/dl and no symptoms or liver enzyme elevation, atorvastatin will be halved. If subject has symptoms or AST/ALT elevation per safety protocol, atorvastatin will be stopped. This process will be repeated at 5, 8 and 12 months and every 4 months after throughout the study.

B.7. Niacin Dosing Up Schedule

Based on our 20 years of experience of using niacin in our previous studies, we designed a dosing-up schedule to help subjects to build the niacin tolerance and to better handle the side effects. This will also help to define a tolerable dose for each subject.

Medication initiation: take 500 mg, 1 tablet, with dinner daily.

1-month F/U visit: take 1000 mg, 2 tablets, with breakfast and dinner daily.

2-month F/U visit: take 1500 mg, 3 tablets, 1 at breakfast and 2 with dinner daily.

[figure not shown]
3-month F/U visit: take 2000 mg, 4 tablets, 2 with breakfast and 2 with dinner daily.

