Glucose Safety:	If 126-159 mg/dl	Careful monitoring	If 126-159 mg/dl	Careful monitoring	If 126-159 mg/dl	Careful monitoring
	If ≥ 160 mg/dl	Letter to PCP & repeat test within 1 M	If ≥ 160 mg/dl	Letter to PCP & repeat test within 1 M	If ≥ 160 mg/dl	Letter to PCP & repeat test within 1 M
	If >200 mg/dl	Repeat test within 2 Wk. Half niacin dose	If >200 mg/dl	Repeat test within 2 Wk. Half niacin dose	If >200 mg/dl	Repeat test within 2 Wk. Half niacin dose
	If >240 mg/dl	Glucose monitoring & stop niacin	If >240 mg/dl	Glucose monitoring & stop niacin	If >240 mg/dl	Glucose monitoring & stop niacin

ULN=Upper Limit of Normal

In addition, the following Table (**Dosage Adjustment Protocol for CPC**) provides basic guidance for dosage adjustment related to both reaching LDL-C and HDL-C targets and dealing with potential drug side effects.

Dosage Adjustment Protocol for CPC (Updated 01Aug2010)

	Sample at 3 months		Sample at 5 months		Sample at 8 months		Sample at 12 months and all visits thereafter	
Single	Target	Strategy	Target	Strategy	Target	Strategy	Target	Strategy
			If >80 ,		If >80 ,		If >80 ,	

Rx Group:	LDL-C ≤ 80 mg/dl	--	LDL-C ≤ 80 mg/dl	double statin dose, or (max dose 80mg)	LDL-C ≤ 80 mg/dl	double statin dose, or (max dose of 80mg)	LDL-C ≤ 80 mg/dl	double statin dose, or (max dose 80mg)
Double Rx Group:	LDL-C ≤ 80 mg/dl	--	HDL-C+5 from base.	Improve compliance	HDL-C+8 from base.	Improve compliance	HDL-C+10 from base.	Improve compliance
	--	--	LDL-C ≤ 80 mg/dl	If >80 mg/dl, double statin dose, or (max. dose 80 mg)	LDL-C ≤ 80 mg/dl	If >80 mg/dl, double statin dose, or (max. dose 80 mg)	LDL-C ≤ 80 mg/dl	If >80 mg/dl, double statin dose, or (max. dose 80 mg)
Triple Rx Group:	--	--	HDL-C+5 from base.	Improve compliance	HDL-C+8 from base.	Improve compliance	HDL-C+10 from base.	Improve compliance
	LDL-C ≤ 60 mg/dl	--	LDL-C ≤ 60 mg/dl	If >60, double statin dose, or (max. dose 80)	LDL-C ≤ 60 mg/dl	If >60, double statin dose, or (max. dose 80)	LDL-C ≤ 60 mg/dl	If >60, double statin dose, or (max. dose 80)
LDL Safety:	If SX/LCF or LDLC < 25	Half statin dose or stop meds	If SX/LCF or LDLC < 25	Half statin dose or stop meds	If SX/LCF or LDLC < 25	Half statin dose or stop meds	If SX/LCF or LDLC < 25	Half statin dose or stop meds

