	If ASX and LDLC < 40	Careful monitoring	If ASX and LDLC < 40	Careful monitoring	If ASX and LDLC < 40	Careful monitoring	If ASX and LDLC < 40	Careful monitoring
	If SX and LDLC < 40	Half statin dose or stop meds	If SX and LDLC < 40	Half statin dose or stop meds	If SX and LDLC < 40	Half statin dose or stop meds	If SX and LDLC < 40	Half statin dose or stop meds

SX=symptomatic, ASX=asymptomatic, LCF=low cholesterol flu-like symptoms including muscle aching, nausea and fatigue.

Please note that renal function monitoring is described under Carotid Imaging Protocols below.

D. Carotid Imaging Protocols

[figure not shown]
D.1. MRI Scan Protocol:

Prior to the carotid MRI scans, subjects will be required to fill-out the *Magnetic Resonance (MR) Procedure Screening Form provided by the MRI center (Attachment 1)*. This form will be reviewed by both the study coordinator and by the MRI center staff

to ensure subject's eligibility for MRI scans. For subjects with coronary stents, we will check MRI safety compatibility of a particular stent or surgical implant by visit www.mrisafety.com or contacting the manufacturer directly.

Subjects from the UW and Yakima sites will receive their carotid MRI scans at the Bio-Molecular Imaging Center (BMIC) ([name], Director) for high-resolution animal and human imaging. A 3T Philips Achieva Quasar Dual 3.0T (Software Release 1.2.2) whole body scanner is available for use at this center as a full time research scanner. This scanner also includes the Philips ViewForum Workstation (Software Release 4.1). Subjects enrolled at the USC site will receive their MRI scans at the USC Imaging Center of Department of Radiology using a standard scan protocol designed by the Vascular Imaging Lab at the University of Washington.

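### For LDL-C below 25 mg/dl, section B.6 and the LDL Safety rows of the dosage table give conflicting statin instructions, and two of the table's own rows overlap

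*Combined protocol and SAP*

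**What the plan says.** Section B.6, under titration down, divides low LDL-C into two bands and gives instructions by symptom and liver-enzyme status.

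- Between 25 and 40 mg/dl, no symptoms, normal enzymes: "If subject's LDL-C < 40 mg/dl and > 25 mg/dl with normal AST/ALT lab values and does not report nausea or fatigue, careful monitoring will" follow, and the dose is left unchanged.
- Between 25 and 40 mg/dl, with symptoms or raised AST/ALT: "atorvastatin will be halved or stopped depending on the decision of the investigator".
- Below 25 mg/dl, no symptoms, no enzyme elevation: "If subject's LDL-C < 25 mg/dl and no symptoms or liver enzyme elevation, atorvastatin will be halved".
- Below 25 mg/dl, with symptoms or raised AST/ALT: "If subject has symptoms or AST/ALT elevation per safety protocol, atorvastatin will be stopped".

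The Dosage Adjustment Protocol table in C.3 has three LDL Safety rows, identical in all four visit columns.

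- Row 1: "If SX/LCF or LDLC < 25", with the strategy "Half statin dose or stop meds".
- Row 2: "If ASX and LDLC < 40", with careful monitoring as the strategy.
- Row 3: "If SX and LDLC < 40", with the same strategy as row 1.

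The table is introduced as an addition that gives basic guidance. Neither place says that it overrides the other, or that the rows are to be read in order.

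**The concern.** A dose-reduction and stopping rule should return one instruction for one clinical state. Here two parts of the protocol answer the same question differently, and the table also answers it in two ways. Staff could follow one part faithfully and depart from the other.

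The rule is applied often. B.6 calls for it at months 3, 5, 8 and 12 and every 4 months thereafter. The trial is open-label (A.2) and runs at three operating sites (A.5), so nothing in the wording makes two sites act alike on the same result. What is at stake is the safety of participants with very low LDL-C and consistent handling of them.

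**Working it through.** No sample-size, power or alpha figure is involved. The check takes each rule literally and lists the actions it triggers at three illustrative LDL-C values: one below 25 mg/dl, one at 25 and one between 25 and 40.

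| LDL-C (mg/dl) | Status | B.6 | Row 1 | Row 2 | Row 3 |
|---|---|---|---|---|---|
| 20 | asymptomatic, AST/ALT normal | halve | halve or stop | monitor | – |
| 20 | asymptomatic, AST/ALT raised | stop | halve or stop | monitor | – |
| 20 | symptomatic | stop | halve or stop | – | halve or stop |
| 25 | asymptomatic | no rule | – | monitor | – |
| 25 | symptomatic | no rule | halve or stop | – | halve or stop |
| 30 | asymptomatic, AST/ALT normal | monitor | – | monitor | – |
| 30 | asymptomatic, AST/ALT raised | halve or stop | – | monitor | – |
| 30 | symptomatic | halve or stop | halve or stop | – | halve or stop |

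Five things follow.

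1. **Asymptomatic, below 25.** Rows 1 and 2 both apply and disagree. Row 2 lacks the lower bound of 25 that B.6 puts on its monitoring band. With normal enzymes, B.6 fixes halving, row 1 adds stopping and row 2 adds monitoring.
2. **Symptomatic, below 25.** B.6 fixes stopping. Rows 1 and 3 also permit halving.
3. **AST/ALT.** B.6 changes its instruction when enzymes are raised; the LDL Safety rows do not mention them. The separate Lab Safety Monitoring table in C.3 deals with AST/ALT without reference to LDL-C, so it does not link the two.
4. **Which drugs.** B.6 speaks of atorvastatin only. Row 1 refers to the statin dose and then, more broadly, to stopping meds. In C.3 the corresponding entry for AST/ALT at three times the upper limit summarises a text step that applies to the study medications generally. The wider meaning is therefore possible here too.
5. **Exactly 25.** Both B.6 bands exclude this value; the table assigns it an action through rows 2 and 3, and row 1 if symptomatic.

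Number of scheduled occasions for the rule: 4 (months 3, 5, 8, 12) + (36 − 12)/4 = 10 through month 36, and 4 + (132 − 12)/4 = 34 through month 132. These count occasions to apply the rule, not expected results below 25 mg/dl.

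**The case against.** The best defence is that row 1 is less specific than B.6 but compatible with it. It pools the two states below 25 and lists both outcomes, so anyone following B.6 stays within row 1. On this view, row 2 is simply the 25 to 40 band with its floor left off, and the table is only guidance. B.10 has prescriptions generated from the atorvastatin dosage determination and signed by the study doctor, which points to B.6 as the working rule. A safety monitor is also told of abnormal results.

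Part of this stands. Following B.6 never breaches row 1, and row 2 may well be a drafting omission. But the reverse does not hold: a site following the table can halve where B.6 says stop, or monitor where B.6 says halve. Reading the rows in order is not stated and fits poorly, because row 1 already catches every symptomatic subject and would leave row 3 with nothing to do. B.6 grants investigator discretion expressly between 25 and 40 and fixes one action per state below 25, so the table reopens a choice that B.6 had closed. The pointers also run both ways: E.3 says that abnormal results are handled under the safety monitoring protocol, and this table stands in the safety monitoring section.

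A reader might also infer that the triple-therapy arm, with its lower target and added ezetimibe, would have most of the results below 25, so that uneven handling would distort the LDL-C contrast behind Aim 4. The documents give no LDL-C distribution on treatment and no frequency of such results, so this cannot be asserted.

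**Conclusion.** The protocol contradicts itself on a dose-reduction and stopping rule for LDL-C below 25 mg/dl. The three-way conflict of monitoring, halving or stopping is confined to asymptomatic subjects; for symptomatic subjects it is stopping against halving or stopping. The missing AST/ALT trigger and the unclear scope of stopping add to it. The gap at exactly 25 is minor: it would be wrong to infer that no instruction exists, since the table supplies one.

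The conclusion rests on the literal wording and on the absence of any statement about which part prevails. With normal AST/ALT, text and table agree for asymptomatic subjects between 25 and 40. No endpoint, analysis or power figure changes, and the number of participants affected cannot be estimated. The correction should be made on grounds of safety and consistent application. No view is taken on which action is right.

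**What to change.** The sponsor's clinicians should reconcile the titration-down paragraph of B.6 with the three LDL Safety rows, so that:

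- each combination of LDL-C band and symptom or AST/ALT status has one instruction, the same in both places;
- the bands do not overlap, and the value 25 mg/dl belongs to one of them;
- the drug or drugs to be reduced or stopped are named identically;
- one sentence says which part governs if a difference remains.

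The choice of action is theirs. The cost is the wording of one paragraph and three table rows, repeated across four visit columns. The design, sample size and analysis are untouched.
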